# 8.4.1.3 Change in Bone Marrow Fibrosis Grade

Grade of bone marrow fibrosis was assessed by investigators according to the European consensus grading system. The proportion of subjects who achieve a reduction of at least 1 grade in bone marrow fibrosis from baseline at any time will be summarized. The bone

marrow fibrosis grade reduction of at least 1 grade at Week 24 will also be summarized. Data after post-study treatment or disease progression will be excluded from the analysis.

Subjects with missing bone marrow fibrosis grade (either baseline or post-baseline) or those with bone marrow fibrosis Grade 0 at baseline are excluded in the analysis for the change in bone marrow fibrosis grade.

Time to 1st achieving a reduction of at least 1 grade in bone marrow fibrosis from baseline will also be summarized. Mean and median time (week) of time to 1st achieving a reduction of at least 1 grade in bone marrow fibrosis from baseline will be provided.

#### 8.4.2 Main Analyses of Secondary Efficacy Endpoints

TSS50W24 rate, anemia response rate and the bone marrow fibrosis grade reduction rate will be estimated. The corresponding 95% confidence interval (Cl) will be provided using Clopper-Person method.

[figure not shown]
Bone marrow fibrosis grades will be tabulated using a shift table with baseline values of Grade 0, Grade 1, Grade 2, Grade 3, or missing grade, versus minimum post-baseline of Grade 0, Grade 1, Grade 2, Grade 3, or missing grade.

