- Hematology and Chemistry: Screening, Pre-dose on Day 1, Weeks 1, 2, 3, 4, 6, 8, 12, 16, 20, 24 and a12 weeks thereafter
- Hematology: 4 hours after the first dose of navitoclax on Day 1, 24 hours post-first-dose on Day 2, and prior to navitoclax dose increases, reductions, or re-initiation after interruption.

Clinic/Efficacy Evaluation visits:

- Clinic Assessments (including spleen and liver palpation): Screening, Day 1, Weeks 1, 2, 3, 4, 6, 8, 12, 16, 20, 24 and q12 weeks thereafter
- MFSAF version 4.0 diary: Daily beginning at the Screening Visit, including pre-dose on Day 1 through the Week 36 Visit. For subjects enrolled in Cohorts 1b and 3 the screening period should be long enough to ensure at least 7 days to collect the daily MFSAF version 4.0 prior to Day 1
- EORTC QLQ-C30 QOL questionnaire: Screening, pre-dose on Day 1, Weeks 4, 8, 12, 24, every 12 weeks thereafter and at the TCV
- PROMIS Fatigue SF 7a questionnaire: Screening, pre-dose on Day 1, Weeks 4, 8, 12, 24, every 12 weeks thereafter and at the TCV
- PGIC questionnaire: pre-dose on Weeks 4, 8, 12, 24, every 12 weeks thereafter and at the TCV
- Imaging for spleen assessment: Screening, Weeks 12, 24, 36, 48, 72 and 96. After 96 weeks of treatment, an MRI/CT should be performed if disease progression is suspected.
- Bone marrow biopsy and aspirate: Screening, Weeks 12, 24, 48 and 96. After 96 weeks of treatment, bone marrow sampling should be performed if disease progression is suspected.
- Disease Assessment based on modified IWG: will be performed at Week 12, 24, 36, 48, 72 and 96. Disease assessment should also occur at any other time if disease progression is suspected or when imaging/bone marrow sampling is performed.

Pharmacokinetic samples will be collected and analyzed throughout the study. Additional samples will be collected for approximately 10 subjects in Cohort 1b who agree to provide blood samples to assess drug-drug interactions between navitoclax and ruxolitinib.

Exploratory biomarker specimens will be collected throughout the study. Analyses may include, but are not limited to allelic burden, mutational status, cytokines, and/or characterization of Bcl-2 and associated proteins.

Diagnosis and Main Criteria for Inclusion/Exclusion:

Key Inclusion:

- Subjects ≥ 18 years of age
- Subjects with documented diagnosis of Primary MF, PPV-MF or PETMF as defined by the World Health Organization classification

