3.4 Navitoclax Clinical Data

Three Phase 1/2a clinical trials investigating the safety, pharmacokinetics, and efficacy of navitoclax in subjects with relapsed or refractory lymphoid malignancies, subjects with small cell lung cancer or other non-hematological malignancies and subjects with chronic lymphocytic leukemia (CLL) are underway or completed.

Preliminary aggregate clinical data from 2 ongoing Phase 1 studies support that navitoclax is tolerable at doses up to 250 mg in a CLL population and up to 325 mg in a lymphoid malignancy population (which includes CLL/SLL subjects). These studies were utilizing a 21/21 day dosing schedule (subjects dosed for 21 consecutive days of a 21-day cycle following a 7 to 14 day lead-in period). Anti-tumor activity has been noted in study subjects with CLL/SLL across the dose ranges tested, suggesting that navitoclax may provide a clinical benefit to these subjects.

As of 28Feb2020, a total of 34 subjects with MF (Cohort 1a) have been treated in the navitoclax in combination with ruxolitinib in Study M16-109. To date adverse events observed occurred at an incidence that appears to be consistent with what has been observed in navitoclax clinical studies and with this population of patients with MF. The most common adverse events of any Grade in Study M16-109 to date are thrombocytopenia (88%), diarrhea (68%) and fatigue (62%). Serious adverse events were reported in 13 subjects (38%) including pneumonia (n = 4), splenic infarct (n = 2), and the following events with 1 occurrence each: anemia, angina pectoris, abdominal pain, colitis, vomiting, chest pain, pyrexia, biliary colic, hyperbilirubinemia, portal vein thrombosis, abnormal liver function tests, gout, respiratory failure and deep vein thrombosis.

Efficacy data from Study M16-109 is available for 34 subjects (Cohort 1a). Spleen Volume Reductions of \geq 35% at Week 24 (SVR_{35w24}) were observed in 27% (9/34) of subjects. Improvements in bone marrow fibrosis have been reported in 29% (10/34) of subjects.

For further details, please refer to the Investigator's Brochure for additional information regarding navitoclax clinical studies, safety and efficacy data, pre-clinical toxicology, metabolism, and pharmacology.

3.5 **Differences Statement**

This is the first study to evaluate navitoclax in subjects with myelofibrosis.

3.6 **Benefits and Risks**

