8.3.1 Efficacy

 SVR_{35w24} will be calculated as the proportion of subjects who achieve $\geq 35\%$ reduction from baseline in spleen volume at Week 24 (SVR_{35w24}). The point estimates of SVR_{35w24}

will be provided. The exact 95% confidence intervals as derived by the Clopper-Pearson method will also be presented. In addition, absolute and percent change from baseline of spleen volume will be summarized with mean, standard deviation, median, minimum and maximum reported. TSS response (at least 50% reduction) rate will be calculated as the proportion of subjects who achieve at least 50% reduction in TSS at Week 24 from baseline. The point estimates of TSS response rate at Week 24 will be provided and corresponding exact 95% confidence intervals as derived by the Clopper-Pearson method will be presented.

Anemia response rate and corresponding exact 95% confidence intervals as derived by the Clopper-Pearson method will be presented.

Descriptive statistics for change in grades of bone marrow fibrosis will be reported.

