- For visits with bone marrow sampling, hematology and chemistry labs should be performed on the same day as the bone marrow assessment. Bone marrow biopsy and aspirate as well as cytogenetics will be performed at Screening (results from historical bone marrow samples will not be accepted), Weeks 12 (D85), 24 (D169), 48 (D337) and 96 (D673). All bone marrow sampling must be completed within the ± 7 day window for the study visit. Additional bone marrow sampling and cytogenetics should be performed if disease progression is suspected, at the discretion of the investigator.
- Procedure should be performed if the subject discontinues from the study for a reason other than documented disease progression and if this procedure has not been done within the last 12 weeks.
- MRI (CT allowed if MRI is medically contraindicated), Bone Marrow sampling and Disease Response Assessments to be performed during Post-Treatment FU visits as necessary if disease progression is suspected.
- May be obtained from bone marrow or peripheral blood sampling.
- Bone marrow biopsy/aspirate samples for exploratory biomarker analysis should be split from the samples collected for local clinical assessment. All bone marrow sampling must be completed within the \pm 7 day window for the study visit.
- See Table 7 and Appendix D for the schedule of Pharmacokinetic Assessments for Navitoclax and Ruxolitinib.
- Cohort 1b-DDI only. See Appendix D Table 8.
- Cohort 1b-DDI only for Days 7 and 8. See Appendix D Table 8.
- MRI/CT of the abdomen to determine spleen volume will be conducted at Screening, Weeks 12 (D85), 24 (D169), 36 (D253), 48 (D337), 72 (D505) and 96 (D673). Additional MRI/CT should be performed if disease progression is suspected, at the discretion of the investigator. All MRI/CT assessments must be completed within the \pm 7 day window for the study visit. All MRI/CT must be sent to a central imaging vendor.

obbyje Navitoclax (ABT-263) M16-109 Protocol Amendment 11

EudraCT 2017-001398-17

Table 6. Study Procedures - Navitoclax Alone or in Combination with Ruxolitinib (Continued)

- ff. Disease Response Assessment to be performed at Weeks 12 (D85), 24 (D169), 36 (D253) 48 (D337), 72 (D505) and 96 (D673). For disease assessments performed at Week 36 and 72, a repeat bone marrow biopsy is not required unless disease progression is suspected. The prior bone marrow assessment may be used for the purposes of assessing disease response per modified IWG criteria.

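### Apart from the Week 24 reduction rate, the SAP summarises marrow fibrosis by the best post-baseline grade and reports no rate of worsening

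*SAP*

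**What the plan says.** Protocol 8.2.2 makes change in marrow fibrosis grade a secondary endpoint. Protocol 8.3.1 gives the analysis no direction: "Descriptive statistics for change in grades of bone marrow fibrosis will be reported". The biopsy schedule in the Protocol synopsis is: "Bone marrow biopsy and aspirate: Screening, Weeks 12, 24, 48 and 96"; Appendix C repeats it and allows extra sampling if progression is suspected.

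The SAP plans four summaries.

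- **Any-time rate (8.4.1.3):** the proportion with a "reduction of at least 1 grade in bone marrow fibrosis from baseline at any time will be summarized". No confirmation is required.
- **Week 24 rate (8.4.1.3):** "marrow fibrosis grade reduction of at least 1 grade at Week 24 will also be summarized".
- **Time to first reduction (8.4.1.3):** time to first "achieving a reduction of at least 1 grade in bone marrow fibrosis from baseline will also be summarized".
- **Shift table (8.4.2):** baseline grade "versus minimum post-baseline of Grade 0, Grade 1, Grade 2, Grade 3, or missing grade".

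Grades are those of the investigator (SAP 8.4.1.3). Protocol 5.1 makes central pathology reading optional, and the SAP fibrosis analysis does not use it. Subjects with a missing grade or with MF-0 at baseline are left out. SAP 8.4.2 attaches a Clopper-Pearson interval to the reduction rate without saying whether the any-time or the Week 24 rate is the main one.

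**The concern.** Three of the four summaries rest on the best or the first favourable reading, and the fourth counts reductions only. None gives the proportion whose grade rose, a last or worst grade, or a shift by visit. Worsening is not picked up elsewhere, because a rise in fibrosis grade is not among the progression criteria in Protocol Appendix E or SAP Appendix B.

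This matters because Protocol 5.6 uses marrow fibrosis to argue for possible disease modification and for Cohort 3. The study is open-label and uncontrolled, with local grading. A rate of falls in grade is hard to interpret without the matching rate of rises.

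The any-time rate also depends on follow-up. SAP 11.0 analyses each cohort once its subjects have completed Week 24 or discontinued, alongside summaries from the other cohorts. Cohort 1a was fully enrolled by 10 April 2019 (Protocol 5.1). Cohorts shown side by side can therefore have had different numbers of chances to improve.

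**Working it through.** **The only fibrosis figure in the documents.** Protocol 3.4 states: "Improvements in bone marrow fibrosis have been reported in 29% (10/34) of subjects". 10/34 = 29.4%, which agrees. Its Clopper-Pearson 95% interval is 15.1% to 47.5%. The text does not say whether this is an any-time or a Week 24 rate, or how many biopsies each subject had.

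**What the minimum-grade table can show, with no reading error.** Take a subject at MF-2 who truly moves to MF-3 and stays there, with four post-baseline biopsies. The minimum exceeds baseline only if all four readings do.

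| True worsening starts at | Shown as worse, minimum grade | Shown as worse, maximum grade |
|---|---|---|
| Biopsy 1 (Week 12) | 100% | 100% |
| Biopsy 2, 3 or 4 | 0% | 100% |

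**What reading error alone can produce.** Assumptions, none of them from the documents: true grade constant; each reading, baseline included, independently one grade too low with probability e and one too high with probability e; readings bounded at MF-0 and MF-3. Subjects read MF-0 at baseline are dropped, as in SAP 8.4.1.3. With e = 0.10:

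- *True MF-2* (read MF-1, MF-2, MF-3 with probability 0.1, 0.8, 0.1).
  - Improved at one biopsy: 0.8×0.1 + 0.1×0.9 = 0.170.
  - Improved as best of four: 0.8×(1−0.9⁴) + 0.1×(1−0.1⁴) = 0.3751.
  - Worse in the minimum table with four: 0.8×0.1⁴ + 0.1×0.9⁴ = 0.0657.
- *True MF-3* (read MF-2, MF-3 with probability 0.1, 0.9).
  - Improved at one biopsy: 0.9×0.1 = 0.090.
  - Improved as best of four: 0.9×(1−0.9⁴) = 0.3095.
  - Worse in the minimum table: 0.1×0.9⁴ = 0.0656.
- *True MF-1*: the same improvement terms as MF-2 (0.170 and 0.3751); worse in the minimum table 0.8×0.1⁴ = 0.0001. One tenth are read MF-0 at baseline and drop out.

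For shares w1, w2, w3 of true MF-1, MF-2 and MF-3, each result is the weighted sum divided by 1 − 0.1×w1. For 20/40/40, best of four is (0.6×0.3751 + 0.4×0.3095)/0.98 = 35.6%.

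| Assumed mix MF-1/2/3 (%) | Improved, one biopsy | Improved, best of four | Worse, minimum table (four) |
|---|---|---|---|
| 20/40/40 | 14.1% | 35.6% | 5.4% |
| 10/30/60 | 12.3% | 33.9% | 6.0% |
| 0/50/50 | 13.0% | 34.2% | 6.6% |
| equal thirds | 14.8% | 36.5% | 4.5% |
| 25/50/25 | 15.4% | 36.8% | 5.1% |

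I quote these as about 12–16%, 34–38% and 4–7%, to leave a margin for other mixes. A cohort entirely at one true grade falls further out: 9.0% and 31.0% improved at MF-3; 0.170/0.9 = 18.9% and 0.3751/0.9 = 41.7% at MF-1.

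**Sensitivity to e (first four mixes).**

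| e | Improved, one biopsy | Improved, best of four | Worse, minimum table (four) |
|---|---|---|---|
| 5% | 7–8% | 19–21% | 3–4% |
| 15% | 17–21% | 44–48% | 6–8% |

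At e = 10%, two biopsies give 21–23% improved and three give 28–30%, so the rate climbs with follow-up. A single biopsy shows 11–13% worse beside 12–15% improved, so both directions of noise would be visible at Week 24.

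**The case against.** **The Week 24 rate.** It is planned, sits at a fixed time and has no best-of-several selection. This stands. It still counts reductions only, and the SAP does not name it as the main rate.

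**The shift table does have cells for worsening.** They hold anyone whose post-baseline grades are all above baseline, including a subject with one, worse, biopsy and a subject with sustained worsening from Week 12. A reader might infer that worsening is almost impossible to see. The table above does not support that: reading error alone puts about 4–7% in those cells with four biopsies. A much smaller figure, 0.1⁴ = 0.01%, appears only if the baseline reading is treated as free of error, which is not reasonable when it is read in the same way as the rest.

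**The protocol still promises direction-neutral descriptive statistics.** True, but Protocol 8.3 leaves the details to the SAP, and the SAP specifies none that gives a rate of increase.

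**The analysis is descriptive.** Protocol 8.3 plans estimation without formal tests, so no error rate or power is affected. Reporting any-time response beside Week 24 also matches how the SAP treats spleen volume. Both stand, and they make this a matter of balanced reporting.

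**A worst-grade table has the opposite bias.** With four biopsies and 10% error it would show 20–26% falsely worse. That is a good reason not to make it the main table.

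**Conclusion.** The point holds in a limited form. The SAP narrows a direction-neutral endpoint to improvement. Its only shift table misses worsening that starts after the first biopsy, and its any-time rate grows with the number of biopsies. That much follows from the text alone.

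The size is an illustration. With 10% independent error in each direction and no true change, best-of-four reading gives roughly 34–38% apparent improvement against 12–16% at one biopsy. Error rate, independence and grade mix are all assumed.

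A reader might infer that the 29% reported for Cohort 1a is reading noise, since 10% error with about three biopsies gives a similar rate. The documents do not support that. They give no reading-error rate and do not define the 10/34. Its denominator is all 34 subjects, whereas the SAP drops those with missing grades, so it need not be the SAP statistic. Nor do the documents say that the any-time rate will be the featured one.

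**What to change.** - **SAP 8.4.2:** add a baseline-to-Week-24 shift table giving numbers improved, unchanged and worsened by at least one grade. Add a shift to the last on-treatment grade. The laboratory shift tables in SAP 9.3.1 already use maximum or final values, so the format is familiar.
- **SAP 8.4.1.3:** report the proportion with an increase of at least one grade at Week 24, with its Clopper-Pearson interval, beside the Week 24 reduction rate. Name the Week 24 rate as the main fibrosis rate. Label the any-time rate, time to first reduction and minimum-grade table as supportive.
- **Optional:** a shift to the worst post-baseline grade, shown beside the best-grade shift so that the two opposite biases are read together.

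Cost: SAP wording and one or two extra tables from data already collected. The reported fibrosis figure would look less favourable if the any-time rate would otherwise have been featured.

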#### 8.5 Exploratory Efficacy Analyses

#### 8.5.1 Exploratory Efficacy Endpoints

8.5.1.1 Spleen Volume Reduction  $\geq$  10%,  $\geq$  20%, 30%, and  $\geq$  35% at Any Time (SVR10, SVR20, SVR30 and SVR35), Spleen Volume Reduction  $\geq$  10%,  $\geq$  20%, and  $\geq$  30% at Week 24

SVR10, SVR20, SVR30, and SVR35 rates at any time are defined as the proportion of subjects who achieved at least 10%, 20%, 30%, and 35% reduction from baseline spleen volume any time, respectively. SVR10, SVR20, and SVR30 at Week 24 are defined as the proportion of subjects who achieved at least 10%, 20%, and 30% reduction from baseline spleen volume at Week 24, respectively. Data after the start of post-study treatment or disease progression will be excluded from these analyses. Subjects who do not have

percent change from baseline (missing baseline or missing post-baseline) in spleen volume will be treated as non-responders. In addition, time to first SVR  $\geq$  10%, first SVR  $\geq$  20%, first SVR  $\geq$  30%, and first SVR  $\geq$  35% will also be summarized.

Above exploratory endpoints will be analyzed in the Full Analysis Set.

#### 8.5.1.2 Duration of SVR35

Only subjects who achieved SVR35 will be included in this analysis for duration of SVR35. The Duration of SVR35 is defined as the number of days from the first date of SVR35 achievement to the first date of 1) SVR< 35% AND observing  $\geq$  25% spleen volume increase from nadir (the lowest spleen volume in the previous assessments) or 2) disease progression (relapse or progressive disease) per investigator by IWG/MRT criteria, whichever is earlier. Subjects without the defined event mentioned above will be censored at the last date of the following assessments on or before post-study treatment: MRI/CT scan for spleen volume assessment, bone marrow assessment, lab assessment, disease response assessment.

[figure not shown]

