During treatment, all assessments must be performed on the day of the specified visit unless a time window is specified in the schedule of assessments (Appendix C). Refer to Section 3.6 for study visit modifications.

Subjects will continue their treatment until end of clinical benefit, unacceptable toxicity or subject meets other protocol criteria for discontinuation (whichever occurs first). All subjects will have a TCV performed when treatment is discontinued.

Response and progression will be assessed by the Investigator based on the modified International Working Group-Myeloproliferative Neoplasms Research and European Leukemia Net (IWG-MRT/ELN) and as noted in Appendix E.²⁴ Spleen volume will be assessed by an independent central review and interpretations will be transmitted to investigators, as available, and will be utilized in determining response and progression. The evaluation of fibrosis grading and reticulin staining grading may be assessed independently by a central pathologist. Independent interpretations of bone marrow samples are not planned to be transmitted to investigators. Details regarding the determination of clinical response and disease progression are provided in Appendix E.

Follow-Up

Safety Follow-Up: All subjects will have one Safety Follow-up visit approximately 30 days following TCV.

Post-Treatment Follow-Up: For subjects who discontinue study treatment for reasons other than disease progression, a Post-Treatment Follow-up visit will be performed approximately 12 weeks following TCV, then every 12 weeks thereafter to assess disease

status until criteria are met for discontinuation from study (e.g., disease progression, initiation of post-treatment cancer therapy, or subject refusal of post-treatment follow-up visits).

Once disease progression is confirmed or the subject begins a post-study treatment for MF other than the continuation of ruxolitinib (Cohorts 1a, 1b or 3), the subject will enter the Survival Follow-up phase.

Survival Follow-Up: Survival Follow-up will then be performed approximately every 6 months for up to 5 years after TCV (provided informed consent has not been withdrawn for collection of such information). Survival information (e.g., date and cause of death, details of post-treatment cancer therapies including response and progression) may be collected via telephone calls (e.g., to subject or family member), clinic visits, and/or public database searches.

5.2 **Selection of Study Population**

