## 6.4 Dose intensity (DI) and Relative Dose Intensity (RDI)

An observed dose intensity (ODI) will be derived for each subject who receives the study drug based on how it was actually administered. A planned dose intensity (PDI) will also be derived based on the protocol-specified schedule of the study drug.

For ODI it is calculated as:

[figure not shown]
ODI = 
$$\frac{\text{Actual total dose}}{\text{Actual total duration of treatment exposure (days)}}$$

For PDI it is calculated as:

PDI 
$$=$$
  $\frac{\text{Planned total dose over protocol specified}}{\text{Actual total duration of treatment exposure (days)}}$ 

RDI is defined as: RDI =  $(ODI/PDI) \times 100\%$ .

The RDI will be summarized based on the study drug administration form in EDC. Ruxolitinib administered before the first dose of navitoclax is considered as prior study treatment therapy collected in the Study Cancer Prior Systemic Therapies (Myelofibrosis)

form in EDC for Cohort 1 (Cohorts 1a and 1b). Ruxolitinib administered after the last dose of navitoclax for Cohort 1 (Cohorts 1a and 1b) is considered as post-study treatment collected in Post Study Drug Systemic Therapies form in EDC.

The actual total duration of treatment exposure in the above equations is defined as the last dose date minus first dose date + 1 for navitoclax or ruxolitinib, respectively. Descriptive statistics will be presented for navitoclax (for all Cohorts) and ruxolitinib (for Cohort 3, Cohort 1a and Cohort 1b) respectively.

Number and percentage of subjects who have dose reductions or interruptions, will be summarized.

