# 8.0 Efficacy Analyses

#### 8.1 General Considerations

The primary analysis population for primary endpoint is the Full Analysis Set. Unless otherwise specified, the secondary efficacy endpoints and exploratory efficacy endpoints will be analyzed in Full Analysis Set.

All efficacy results will be presented by cohort unless stated otherwise. For all analyses, unless otherwise specified, data collected after the cutoff date will be excluded from statistical analysis. All spleen volume related endpoints described in Section 3.0 will be based on the assessments from the central review of the radiographic images by an Independent Review Committee (IRC) as described in the protocol.

abbyie Navitoclax/ABT-263

Navitoclax/ABT-263 M16-109 – Statistical Analysis Plan Version 4.0 – 31 January 2023

All response rates and the corresponding 95% confidence interval (Cl) using the Clopper-Pearson method will be provided.

For the analyses of all time-to-event endpoints, survivorship functions will be estimated using Kaplan-Meier product-limit methodology. If reached, median time-to-event and its 95% CI will be presented.

For the analyses of all continuous endpoints, such as change from baseline in score, the scores will be summarized with baseline mean, visit mean, mean change from baseline, mean percentage change from baseline, standard deviation, and the corresponding 95% CIs.

Baseline measurement related to each efficacy endpoint for analysis has been described in Section 7.0.

[figure not shown]
The post-study treatment refers to Post Study Drug Systemic Therapies for Myelofibrosis, Post Study Drug Radiation Therapy and Post Study Drug Transplant. The disease progression (DP) refers to relapse or progressive disease in the Disease Response Assessment Form.

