# 8.5.1.9 Progression-Free Survival (PFS)

PFS is defined as time from the first date of study treatment to the date of first documented disease progression/relapse per IWG criteria as determined by the investigator, or death due to any cause, whichever is earlier. Disease progression and death after start of post-study treatment are not considered as an PFS event.

For subjects who do not experience a PFS event (disease progression, relapse, or death due to any cause) on or prior to the start of post-study treatment, PFS will be censored at the last adequate disease assessment (where IWG response evaluation is not missing) on or prior to the start of post-study treatment.

[figure not shown]
For subjects without any post baseline disease assessments who did not die, PFS will be censored at Day 1.

PFS will be analyzed in the Full Analysis Set.

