# 13.0 Version History

## Table 8.SAP Version History Summary

[figure not shown]
Version	Date	Summary			
1.0	24 Nov 2020	Original version			
1.1	16 Jun 2021	
 
Clarify exclusion of data beyond new anti MF therapy, PD in primary/secondary efficacy analyses.
 
Clarify BL TSS definition.
 
Clarify BL Hemoglobin calculation.
 
Update the definition of anemia response and corresponding duration.
 
Clarify missing data handling in PRO data.
 
Add regression analyses of SVR35W24 vs baseline DIPSS prognostic variables.
 
Add subgroup analyses by age group.
 
Add subgroup analyses for DIPSS INT-1 pts in Cohort 1.
 
Clarify TEAE criteria for AEs on Day 1 and AEs with missing/incomplete dates.
 
Add AESI overview summary.
 
Add AE leading to death summary.
 
Add PK set.
 
Add PK set.
 
Add blood pressure shift summary.
 
Update safety topics of interest table.
 
Clarify sample size per protocol amendment.
 
Other editorial changes.
 
			
2.0	27 Sep 2021	
 
Efficacy evaluable set added
 
SVR35W24 analysis window extended to accommodate schedule challenges due to COVID19.
 
Restrict data up to 30 days post last dose of study drug for anemia response and duration of anemia response.
 
Modification of duration of anemia response derivation.
 
Modify the missing data handling for spleen length to be consistent with SVR.
 
Other editorial changes.
 
			
2.1	18 Oct 2021	
 
Modify the definition of duration of SVR35 to incorporate other objective measure which may indicates the end of response.
 
Update safety topics of interest table.
 
			

[figure not shown]
Version	Date	Summary				
3.0 draft	08 May 2022	1. Modify anemia response, duration of anemia response				
		2. Modify PFS and OS				
		3. Remove analysis of vital signs				
		4. Modify PRBC transfusion analysis				
		5. Modify TSS Week 24 derivation				
3.0	09 Jan 2023	1. Fix typo in version 3 draft				
		2. Efficacy evaluable set removed				
4.0	31 Jan 2023	1. Add DIPSS+ score at study entry				

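### Duration of SVR35 (SAP 8.5.1.2): the start of post-study treatment limits the censoring date but not the events, so read literally the censoring depends on the outcome

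*SAP*

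**What the plan says.** SAP 8.5.1.2 analyses only subjects who reached SVR35. Duration ends at the earlier of two events. The first is a spleen volume reduction back under 35% together with a rise of at least 25% from nadir. The second is "disease progression (relapse or progressive disease) per investigator by IWG/MRT criteria, whichever is earlier". Neither is tied to the start of post-study treatment. The censoring rule is: "Subjects without the defined event mentioned above will be censored at the last date of the following assessments on or before post-study treatment". The estimator comes from SAP 8.1: "survivorship functions will be estimated using Kaplan-Meier product-limit methodology".

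The PFS section, SAP 8.5.1.9, has both halves of such a rule. It censors at the last adequate assessment up to the start of post-study treatment, and it also says: "Disease progression and death after start of post-study treatment are not considered as an PFS event".

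Two further passages decide who is concerned. SAP 6.4 says: "Ruxolitinib administered after the last dose of navitoclax for Cohort 1 (Cohorts 1a and 1b) is considered as post-study treatment". It names the same post-study systemic therapy record that SAP 8.1 uses to define post-study treatment. Protocol 5.1 (Follow-Up) fixes the move to survival follow-up as follows: "Once disease progression is confirmed or the subject begins a post-study treatment for MF other than the continuation of ruxolitinib". A Cohort 1 subject who only continues ruxolitinib therefore stays in the 12-weekly disease follow-up.

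**The concern.** Take two responders who start the same post-study treatment on the same day, both still in response. One later loses response and this is recorded; the other never does. On the wording of 8.5.1.2, the first has a defined event and stays in the risk set until it happens. The second has none and leaves the risk set at or before the treatment start. Who remains at risk after that day is settled by what happens later. Kaplan-Meier requires that being censored carry no information about the future event, and here it does. A larger sample does not remove the problem.

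At stake are the curve and median for duration of spleen response, which serve the stated exploratory objective on duration of disease response. Failures on later therapy would also be charged to the study-treatment response. And two competent programmers could produce different medians from the same text.

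**Working it through.** The documents give no figure for duration of SVR35, so there is none to reproduce.

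**1. Does another rule supply the missing limit?**

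- SAP 8.2 leaves the censoring rules for time-to-event endpoints to the endpoint sub-sections, so 8.5.1.2 has to carry its own.
- SAP 8.1 defines post-study treatment but contains no general exclusion of later data.
- SAP 8.5.1.1 has an exclusion, confined to the SVR rates: "Data after the start of post-study treatment or disease progression will be excluded from these analyses".
- The version 1.1 entry in SAP Table 8 reads "Clarify exclusion of data beyond new anti MF therapy, PD in primary/secondary efficacy analyses". Duration of SVR35 is exploratory.
- SAP 8.6.1 (variant allele frequency) deliberately keeps later data. The SAP decides endpoint by endpoint, so silence has no safe default.

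**2. Can a late event be recorded?** Yes, in Cohorts 1a and 1b, by the ruxolitinib route above. The footnotes to protocol Appendix C, Table 6 call for imaging and response assessment after treatment only when progression is suspected, so what is recorded leans towards failures. Protocol 5.1 also allows progression on later therapies to be collected in survival follow-up. No passage says how often any of this happens.

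**3. Worked example.** Nine responders (protocol 3.4 reports 9 of 34 in Cohort 1a at Week 24). All times are assumed, in months: two lose response at 6 and 10; two are event-free to 24; five start post-study treatment at 8, with an assessment that day. Of those five, two lose response at 14 and 18 and three never do. At each event the estimate is multiplied by 1 − 1/(number at risk).

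| Rule | Calculation | 12 months | 24 months | Median |
|---|---|---|---|---|
| Everyone followed through | 8/9 × 7/8 × 6/7 × 5/6 | 0.778 | 0.556 | not reached |
| Symmetric: all five censored at 8 (as for PFS) | 8/9 × 2/3 | 0.593 | 0.593 | not reached |
| Literal 8.5.1.2: three censored at 8, two kept | 8/9 × 4/5 × 3/4 × 2/3 | 0.711 | 0.356 | 18 |

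If every late event is recorded, the literal rule has the same events as full follow-up and a risk set that is never larger, so its curve can never lie above that one. Against the symmetric rule it can: at 12 months it is higher (0.711 against 0.593), because future failures remain at risk until they fail.

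**4. Simulation.** Assumptions: constant hazards; loss of response 0.03 per month before the start of post-study treatment (true median 0.693/0.03 = 23.1 months); start hazard 0.01, 0.02 or 0.04; loss hazard after the start 0.015, 0.03 or 0.06; follow-up 12 to 48 months; all or half of late events recorded. That makes 3 × 3 × 2 = 18 scenarios of 200,000 responders each.

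- Symmetric rule: median about 23 months, 24-month estimate about 0.49.
- Literal rule, all late events recorded: median 16.8 to 22.3, 24-month estimate 0.33 to 0.47.
- Literal rule, half recorded: median 18.7 to 22.7, 24-month estimate 0.39 to 0.48.

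The literal rule was below the symmetric rule on both measures in all 18. Against full follow-up it was not always lower: with half of late events recorded, start hazard 0.02 and later loss hazard 0.06, its median was 20.5 against 20.0.

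**5. Dependence on recording.** Assumptions: true median 24 months, median time to post-study treatment 18 months, equal hazards before and after, follow-up 24 to 48 months. The symmetric rule gives 23.9.

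| Late events recorded | Literal median (months) |
|---|---|
| 100% | 19.8 |
| 50% | 21.1 |
| 25% | 22.2 |
| 10% | 23.2 |

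**The case against.** The strongest reply is that 8.5.1.2 never says that late events count. Its one mention of post-study treatment restricts the data used, and the subjects without an event could be read as those without one up to that date. Neighbouring response endpoints (SVR rates, palpable spleen, TSS50, ORR, PFS) all cut off there, and programming detail is left to a separate plan. This is a fair reading, but it has to be supplied by the programmer. PFS spells the limit out and this section does not, so the ambiguity is itself a reason to add the sentence.

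Second, late events may be few. After treatment, scans are taken only on suspicion; the first event needs a spleen volume; progression found by palpation needs imaging confirmation (protocol Appendix E, Table 12); and post-treatment visits stop once a new MF therapy begins. This stands. It limits the size and leaves the flaw in place.

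Third, the symmetric rule is not assumption-free. Equal hazards before and after the start make it unbiased by construction, whereas in practice starting a later therapy may itself be informative. Censoring at the start and following everyone through it are different estimands. This also stands: either is defensible, while a mixture that depends on the outcome is not.

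A reader might go further and infer that the case is routine, that the median is understated by about 1 to 12 months, and that some 114 of 174 subjects are affected. The documents do not support this. They give no frequency. The 12-month end comes from one assumed corner (true median 36, start median 12, every late event recorded: 35.9 against 23.5). And 114 is the planned enrolment of Cohorts 1a and 1b (34 + 80), whereas only SVR35 responders enter the analysis and only some of them could be affected.

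**Conclusion.** The point holds as a defect in the rule as written. Followed literally, 8.5.1.2 makes censoring depend on the outcome, and the median and late Kaplan-Meier estimates would generally be too short. It does not follow that the curve is too low at every time point, or that the reported result will be materially wrong.

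The size cannot be derived from the documents. It depends on how many responders start post-study treatment while still in response, their hazard afterwards, and the share of later failures recorded. Under the assumptions of step 5 the median shift runs from 0.7 months (23.9 − 23.2) at 10% recording to 4.1 months (23.9 − 19.8) at full recording, where the 24-month estimate is 0.410 against 0.498. For scale, with an assumed 20 responders and no censoring the standard error of a proportion near one half is √(0.5 × 0.5/20) = 0.11, already more than that shift of 0.09.

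The endpoint is exploratory, no formal test is planned, and SVR35W24 has its own explicit exclusion in SAP 8.3.1, so the primary result is untouched. The sentence is worth adding because the remedy is cheap and the present text permits two different answers.

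**What to change.** Add to SAP 8.5.1.2, in line with 8.5.1.9:

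> Loss of response or disease progression after the start of post-study treatment is not counted as an event; such subjects are censored at the last listed assessment on or before that start.

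The cost is one sentence and one date condition in the program, with no new data. The estimate will rest on fewer events and have a wider interval.

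If the sponsor prefers to count later events, event-free responders must also be kept at risk past the start of post-study treatment. That is harder to support with the planned data, because post-treatment scans are taken only when progression is suspected.
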